1.2 SCHEDULE OF ACTIVITIES (SOA)

Table 1: Schedule of activities for KiT intervention

Time Point	Enrolment/ Randomization (21 month randomization period)	Intervention Period (12 months)				End of intervention
	-1 week	0	3 months	6 months	12 months	
ENROLMENT						
Eligibility screen	X					
Informed consent	X					
Randomization	X					
INTERVENTION*						
Active arm		X	X	X	X	
Control arm						
ASSESSMENTS						
KiT						
Demographics survey		X		X	X	
READY		X		X	X	
SEDM		X		X	X	
Barriers to Diabetes Adherence (BDA) in Adolescence Stigma subscale		X		X	X	
T1D-related hospitalization (OHIP/RAMQ)					X	
T1D-related ED visits (OHIP/RAMQ)					X	
Process Evaluation			X	X	X	
KiT modifications**			X	X		
Cost of implementation analysis			X	X	X	

*only participants in the active arm will receive the KiT intervention during the 12-month intervention period. Both study arms will receive usual medical care during 12-month intervention period.

**will occur in real-time and only if results of process evaluation reveal modifications or adjustments are required to improve user engagement and satisfaction

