3 OBJECTIVES AND ENDPOINTS

The **primary objective** of this study is to compare the effectiveness of a text message-based T1D transition intervention that will personalize transition education and support, as an adjunct to usual T1D transition care versus usual transition care alone on a patient-reported outcome measures (PROM) called the Self-Efficacy for Diabetes Management (SEDM) scale, measured at baseline, 6 months, and 12 months after enrollment in the study.

The **secondary objectives** of this study are to evaluate the impact of this text-messaging based intervention on:

- other patient reported experiences and outcomes (PREMs/PROMs) including the READY tool, a transition readiness assessment for emerging adults with diabetes diagnosed in youth; and the Barriers to Diabetes Adherence in Adolescence (BDA) questionnaire Stigma Subscale for assessing perceived stigma
- self-reported time between final pediatric diabetes visit and first adult diabetes visit
- self-reported and/or lab reported A1c at baseline and at 12 months after enrollment to study (depending on data availability)
- diabetes-related ED visits (measured using self-reported, medical chart and health administrative data)
- diabetes-related hospitalizations (measured using self-reported, medical chart and health administrative data)
- Aggregate and direct medical costs associated with the intervention and its implementation study data and administrative data)
- Exploring how the KiT large language model (LLM) chatbot is used in a real-world setting for more natural conversations and opportunities for us to improve its performance over time. The LLM chatbot is not a learning model and will only utilize existing resources gathered for the KiT study.

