evaluate the impact of this text message-based intervention on the following, compared to the usual transition care alone: 
 • Transition readiness • perceived stigma of living with T1D • self-reported time between final pediatric diabetes visit and first adult diabetes visit • self-reported and/or lab reported A1c at baseline and at 12 months after enrollment to study (depending on data availability) • diabetes related ED visits • diabetes related hospitalization • Cost of implementation • Explore how the KiT LLM chatbot is used in a real-world setting for more natural conversations and opportunities for us to improve its performance over time. The LLM chatbot is not a learning model and will only utilize 	
 • transition readiness measured by the READDY tool at baseline, 6 and 12 months; READDY is a transition readiness assessment for emerging adults with diabetes diagnosed in youth. The READDY tool assesses diabetes-related knowledge or skill items by querying respondents on 42 total items split into 5 domains: knowledge, navigation, health behaviors, and insulin pump skills. Respondents answer on a Likert scale from “yes, I can do this” to “Haven’t thought about it”; confidence level is evaluated in each domain • the Barriers to Diabetes Adherence in Adolescence questionnaire (BDA) Stigma Subscale; in our study, stigma will be defined as an affirmative response to at least one of three key items on this subscale • A1c collected at baseline and 12 months after enrollment to study will be self-reported and/or lab-reported (depending on data availability) • Diabetes related ED visits, hospitalizations, will be measured for the 12 months prior to and 12 months during the intervention using self-reported, medical chart, and health administrative data from ICES. • Costs of implementation • LLM chatbot data 	
 • The READDY tool has been validated during its development by examining its correlation with existing validated transition readiness tools such as TRAQ(40); the READDY tool was favored by the KiT subcommittee that included a patient partner. The KiT subcommittee felt that compared to other transition readiness scales specific to diabetes, the READDY tool was specific and relevant to what is being evaluated and it is patient-reported • the Barriers to Diabetes Adherence in Adolescence questionnaire was developed to measure psychosocial barriers to adherence in adolescents with T1D; the stigma subscale has previously shown to be useful in research and clinical settings(41) • HbA1c: From long-term follow up of the landmark Diabetes Control and Complications Trial (DCCT) participants, early metabolic control has a lasting legacy. Individuals randomized

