4 STUDY DESIGN

4.1 OVERALL DESIGN

First, we **hypothesize** that the intervention will improve diabetes self-efficacy.

We will conduct a **multi-site randomized control trial** to evaluate the effectiveness of an eHealth solution for T1D transition care. The study sample size is 234 adolescents with T1D from 6 pediatric diabetes centres (4 in Ontario and 2 in Quebec) and allocate them 1:1 to the intervention or control arm stratified by site. Participants will be recruited at their pediatric centre within 3-4 months of either their planned final pediatric visit or 18th birthday. We opted for individual randomization the target of the intervention is diabetes self-efficacy during the time between pediatric and adult care and relates to the individual rather than provider or clinic-based practices.

Intervention: both intervention and control groups will receive usual diabetes care including all medical visits and tests. In addition, the intervention group will receive the text messages for diabetes support and resources tailored according to their needs and interest. Both intervention and control groups will also complete PREMs and PROMs at baseline, 6 and 12 months.

Process Evaluation: the embedded process evaluation involves a mixed-methods approach using individual semi-structured interviews alongside user engagement metrics and quantitative outcome data to evaluate how and why the intervention achieved (or failed to achieve) the desired effects and identifying the different paths of engagement (i.e., combinations of KiT components) that produce a positive effect on trial outcomes. Using an embedded single case design with cross case synthesis, the objective of the process evaluation is to gain an in-depth understanding of whether the intervention was received as intended (intervention fidelity), the mechanisms of action, and the conditions and factors associated with initial engagement and sustained use of the intervention.

Health system impact: We will examine health care utilization of patients with T1D using de-identified administrative and, self-reported health data for at least 12 months after study enrolment. We will securely link patients' health card number to provincial administrative databases housed at ICES in Ontario and Med-Echo and Régie de l'assurance maladie du Québec (RAMQ) databases in Quebec.

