7 DISCONTINUATION AND WITHDRAWAL

7.1 DISCONTINUATION OF STUDY INTERVENTION

Discontinuation from KiT intervention does not mean discontinuation from the study, and remaining study procedures should be completed as indicated by the study protocol.

The data to be collected at the time of study intervention discontinuation will include the following:

- The 6-month or 12-month follow-up questionnaires (dependent on which questionnaire was most recently completed), PROMS (SEDM, READDY, BDA)
- Self or lab- reported A1c at baseline and at 12 months after enrollment to study
- diabetes related ED visits and hospitalizations (measured using health administrative data)
- Aggregate and direct medical costs associated with the intervention and its implementation study data and administrative data)

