8.5.3 ANALYSIS OF THE SECONDARY ENDPOINT(S)

For secondary outcomes, continuous data will be reported as means with SDs and between-arm differences in means will be calculated using Student's t-tests or non-parametric statistics. To account for repeated measures, secondary analysis will be conducted to calculate within (baseline, 6 months, 12 months) and between arm-differences to evaluate changes.

We will compare baseline adjusted self-reported mean HbA1c at 12 months between those in the intervention versus control arms. This will be done using linear regression to estimate the effect of the intervention on HbA1c.. The same Bayesian model as the primary analysis will be used. We will adjust for by sex and gender.

From the process evaluation, we will report metrics of user engagement by # of interested topics chosen by the participant, type of specific topics, proactive use of chatbot, response rate (%) to messages that query participants with a question or prompt requiring a SMS response, and proportion (%) of participant clicks on resource and educational links. Furthermore, qualitative observations made during the one-on-one interviews and surveys administered during the process evaluation will be analyzed using thematic analysis strategies guided by HAPA and the TAM, identifying key themes that demonstrate important contextual influences and practices related to the implementation and evaluation of the e-Health technologies in actual contexts of health care delivery. The findings of the qualitative data will be used to develop statements of the relationships between (a) key contextual factors (e.g., perceived needs, outcome expectancies, self-efficacy), (b) the mechanisms by which they affect the implementation of the e-Health interventions, and (c) the impact on the outcomes of the KiT intervention themselves (in Realist Evaluation these statements are referred to as “Context-Mechanism-Outcome Configurations” (43).

For the Coincidence Analysis, we will create individual case constructions for all trial participants that will triangulate intervention engagement data by intervention component with outcome data, using pathways informed by the semi-structured interviews. Where required, variable values will be converted to have categorical properties according to the definitions and criteria developed by the research team. CNA package in R will be used for data analysis.

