- 1) From Medical Charts: first and last name, telephone number and email in order for local research coordinator to establish contact with eligible participants during recruitment phase, either in clinic or virtually via telephone or email. Participant's HbA1c value within 6 months prior to enrollment, mailing address including 6-digit postal code will also be obtained from their medical chart. The full mailing address is needed to send study information letters and/or baseline, 6 month or 12 month reminder letters (if preferred by participant versus email communication). Additionally, the full 6-digit postal code is needed for ICES verification during linkage of participant OHIP number to administrative data sets, and for socioeconomic analysis using the deprivation index , which requires the use of 6-digit postal codes. Diabetes related ED visits, and hospitalizations will be measured for the 12 months prior to enrolment to evaluate the impact of this text message-based intervention, compared to the usual transition care alone. Only local research coordinators will access information from patient medical charts after obtaining local REB approval and institutional approval for this study. PHI data from participant medical charts will be stored on the enrollment log (encrypted and on password-protected computer).
- 2) Provincial Health Card Number: All participant consent forms will indicate that we are collecting OHIP (in Ontario) and RAMQ (in Quebec) numbers in order to perform linkage to provincial administrative data . We will be recording and storing the OHIP and/or RAMQ numbers on a log separate from all other data collection documents and will not enter this information into REDCap or the KiT intervention algorithm, or the enrollment log or Master Linking log. Memotext will not have access to participants' OHIP and/or RAMQ number. Upon study data collection completion, all participating sites will upload their participant OHIP/RAMQ number to a secure file portal in order to enable administrative data linkage via ICES in Ontario and Med-Echo and Régie de l'assurance maladie du Québec (RAMQ) databases in Quebec. To enable

verification of provincial health card number for linkage to administrative datasets, ICES and RAMQ will receive participant full first and last name, Study ID number, OHIP or RAMQ number, full date of birth, sex and full 6-digit postal code.

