Memotext protects personal information by security safeguards appropriate to the sensitivity of information. They are committed to keeping personal information secure, and have appropriate technical, administrative, and physical procedures in place to protect personal information against loss or theft, as well as authorized access, disclosure, copying, use, modification, disposal or destruction. In addition, methods of protection and safeguards include, but are not limited to, locked filing cabinets, restricted access to offices, security clearances, need-to-know access and technological measures including the use of passwords, encryption and firewalls.

Data collection for secondary outcomes measured using administrative data: We will securely link patients' health card number to provincial administrative databases housed at ICES in Ontario and Med-Echo and Régie de l'assurance maladie du Québec (RAMQ) databases in Quebec. The study investigators will be permitted to access de-sensitized information only for analysis (i.e., any information that can directly identify a person like health card number or name will be removed or replaced with a code that is not known to the study investigators). We will measure all diabetes-related hospitalizations, emergency department visits, and HbA1c results (Ontario only from the Ontario Lab Information System (OLIS)), in the 12 months prior to enrollment in the study and for 12 months after enrollment. In Ontario we will also collect information on hospitalizations for DKA or hypoglycemia from the Canadian Institute of Health Information (CIHI) discharge abstract database (DAD) and emergency department visits for hyper/hypoglycemia will be ascertained using the National Ambulatory Clinic Reporting System (NACRs). In Quebec we will measure hospitalizations from Med-Echo (hospitalizations) and RAMQ databases (physician billings from hospitalizations) and emergency department visits for hypo/hyperglycemia will be identified from the RAMQ databases. A data sharing agreement will be in place for this transfer, between ICES and SickKids.

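### The protocol gives conflicting sources for ED visits and hospitalisations, and no named test uses the prior-year count; linked administrative data should be the sole source for the between-arm comparison

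*Protocol*

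**What the plan says.** The protocol describes the source of these two endpoints in several places, and the descriptions do not agree.

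- **Section 3, objectives text:** three sources, "diabetes-related ED visits (measured using self-reported, medical chart and health administrative data", with the same wording for hospitalisations.
- **Section 3, endpoint table:** the same three sources for both years; events "will be measured for the 12 months prior to and 12 months during the intervention using self-reported, medical chart, and health administrative data from ICES". Quebec's databases are not mentioned.
- **Section 4.1:** two sources and no chart: "using de-identified administrative and, self-reported health data for at least 12 months after study enrolment". Here Med-Echo and RAMQ are named beside ICES.
- **Section 1.2 (schedule):** administrative data only: "T1D-related ED visits (OHIP/RAMQ", with a matching row for hospitalisation.
- **Section 7.1:** administrative data only: "diabetes related ED visits and hospitalizations (measured using health administrative data". Section 8.1 also lists both endpoints under administrative linkage.
- **Section 10.1.6.1, medical charts:** "Diabetes related ED visits, and hospitalizations will be measured for the 12 months prior to enrolment". No chart collection of these events after enrolment is described. The schema in 1.1 likewise puts the coordinators' collection of ED and hospital data at baseline.
- **Section 10.1.6.1, administrative data:** hospitalisations and ED visits in both provinces "in the 12 months prior to enrollment in the study and for 12 months after enrollment".

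On analysis, 8.2 states the hypothesis as fewer ED visits and hospitalisations than control at 12 months relative to baseline. For secondary outcomes, 8.5.3 opens with continuous data and says "between-arm differences in means will be calculated using Student's t-tests or non-parametric statistics". It then adds within-arm and between-arm changes over baseline, 6 and 12 months, without naming a model. Of the secondary outcomes, only HbA1c is given a baseline-adjusted model.

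**The concern.** A reader of this protocol cannot tell which source defines an event or what happens when sources disagree. The choice matters because the sources cover different people and periods.

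Self-report comes from participants who know their arm (4.2) and exists only where a questionnaire is returned; 8.3 allows for 20% loss. The intervention arm alone has continuing KiT contact during the year (6.1.1), so recall or response could differ by arm. Chart data are described only for the earlier window, and enrolment takes place close to planned transfer or the 18th birthday (5.1), so some later events may fall in adult care. If either source contributes to the comparison, the before and after counts are ascertained differently, and the arms may be too.

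The second problem is the analysis. A prior-year count is collected in both arms and the hypothesis refers to baseline, yet no named test uses that count. The change analysis is tied to questionnaire visits, which do not match two 12-month windows of counts.

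**Working it through.** **1. The plan's own figure.** The only power statement (8.3) concerns the primary endpoint: 117 per arm, a difference of 0.75 in SEDM, more than 80% power. No rate, effect or power is given for ED visits or hospitalisations, so there is no figure to reproduce for this point.

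**2. Sources side by side.**

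| Source | Year before enrolment | Year after enrolment | Who is covered |
|---|---|---|---|
| Self-report | listed in section 3 | listed in sections 3 and 4.1 | those who return questionnaires; arm known |
| Chart | described (1.1, 10.1.6.1) | listed in section 3, collection not described | participants' charts at the pediatric sites |
| Linked administrative | described (10.1.6.1) | described (10.1.6.1) | all participants consent to use of the health number (10.1.2) |

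Only the last row is fully described in both windows.

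**3. Why ascertainment matters.** If a source captures a fraction c_I of true events in the intervention arm and c_C in control, the expected observed rate ratio is the true ratio × c_I/c_C. Unequal capture biases the comparison whatever the sample size. The documents give no capture fractions, so this part has no number.

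**4. Number analysed.** With 20% loss, 117 × 0.80 = 93.6 per arm have 12-month self-report. If all 117 per arm were linked, the variance would be multiplied by 93.6/117 = 0.80 and the standard error by √0.80 = 0.894. Full linkage is an upper bound, because the protocol documents consent and not linkage success.

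**5. Prior-year count.** With correlation ρ between the two years, adjustment multiplies the variance by 1 − ρ²; a simple change score multiplies it by 2(1 − ρ).

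| ρ (assumed) | Adjusted | Adjusted and full linkage (× 0.80) | Change score |
|---|---|---|---|
| 0.3 | 0.91 | 0.73 | 1.40 |
| 0.5 | 0.75 | 0.60 | 1.00 |
| 0.7 | 0.51 | 0.41 | 0.60 |

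A plain change score therefore loses precision below ρ = 0.5. Under a shared gamma frailty with variance v and mean μ events per year, ρ = μv/(1 + μv). With v = 2 this gives 0.29 at μ = 0.2, 0.44 at 0.4 and 0.55 at 0.6. At μ = 0.1, with v from 1 to 4, adjustment reduces the variance by only 1 to 8%.

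**6. Simulated power.** Assumptions: true rate ratio 0.5, v = 2, 20% loss at random in both arms, 1,000 runs per setting. The count model is Poisson with robust variance and log(prior count + 0.5), without a site term.

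| μ | t-test, completers | t-test, all linked | Count model, all linked, no prior count | Count model with prior count |
|---|---|---|---|---|
| 0.2 | 0.31 | 0.39 | 0.40 | 0.43 |
| 0.4 | 0.48 | 0.57 | 0.60 | 0.68 |
| 0.6 | 0.58 | 0.68 | 0.70 | 0.82 |

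Type I error over the settings run, including one with v = 4, was 0.047 to 0.058 for the t-tests and 0.056 to 0.069 for the count model with the prior count. A small part of its apparent gain is therefore mild inflation.

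**The case against.** The strongest reply is that the operative sections already settle the source. The schedule, 8.1 and the administrative-data part of 10.1.6.1 all point to linkage, and 10.1.6.1 covers both years and both provinces. On that reading, the ICES-only wording is a drafting slip, the chart pull is supplementary, and source precedence and a count model belong in the SAP. Questionnaire reminders and incentives are the same in both arms, and the protocol's descriptions of questionnaire content do not mention ED or hospital events.

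Much of this stands, and it rules out several stronger readings. A reader might infer that the three sources are pooled into one count, or that a chart-based before is compared with a self-reported after; no section says so. A reader might infer that a t-test is fixed for these counts; 8.5.3 is worded for continuous data and allows rank methods. A reader might infer that the prior-year count is ignored altogether; 8.2, 8.5.3 and 10.1.6.1 show that some use was intended. Nor do the documents show that nearly all participants will be linked, or that transfer follows enrolment by a fixed interval: 5.1 sets a window relative to transfer or the 18th birthday.

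The objection does not remove the contradiction. Section 3 is where the endpoint is defined, and it conflicts with 4.1 and with 1.2, 7.1 and 8.1. Leaving detail to a SAP does not tell its author which definition governs. Linkage also has limits: out-of-province events are missed, and capture differs between Ontario and Quebec. Randomisation stratified by site should balance the provincial difference between arms.

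**Conclusion.** The point holds as a contradiction in the definition of two secondary endpoints, together with a gap between their hypothesis and the named tests. It rests on the text and not on the simulation. The risk of unequal ascertainment arises if self-report or chart data enter the comparison, which the protocol allows but does not state that it will do; differences between arms are possible, not shown.

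The precision gain is secondary. Under the assumed rates, dispersion and halving, power rises by 12 percentage points at 0.2 events per year (31% to 43%) and by 24 at 0.6 (58% to 82%). Roughly 8 to 10 points of that come from using all participants rather than completers, and this part assumes complete linkage. The gain from the prior count is small if events are rare. No rank test was compared. The primary endpoint is unaffected.

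**What to change.** In sections 3, 4.1 and 8.5.3, make linked administrative data (ICES in Ontario; Med-Echo and RAMQ in Quebec) the sole source for the between-arm comparison of ED visits and hospitalisations, in both the 12 months before and the 12 months after enrolment. Bring the endpoint table into line with 1.2, 7.1 and 8.1. Keep self-report and chart data as descriptive or supplementary, for example for out-of-province events and for agreement between sources.

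In 8.5.3, state that these counts are compared with a negative binomial or robust-variance Poisson model containing arm, site and the 12-month pre-enrolment count.

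The cost is wording and a standard model; the linkage is already planned. The downsides are that results wait for linkage, out-of-province events are missed, and robust Poisson may show slight type I inflation at this sample size.
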